3.6.3 CsA Dose Selection for Monkey Safety Study

The dose of cyclosporine was based on results of a pharmacokinetic study of i.m. cyclosporine in Cynomolgus monkeys (see Section 3.6.4 below), and a supporting subsequent study also in Cynomolgus monkeys (see Section 3.6.5 also below).

3.6.4 Study Number MPI-004; MPI Research

Three male Cynomolgus monkeys were administered cyclosporine i.m. daily at 15 mg/kg for 4 days. Blood samples for analysis of cyclosporine levels were taken at 0 hr., 1 hr., 2 hr., 3 hr., 5 hr., 8 hr. 12 hr., and 24 hrs. on days 1, 2, and 3 at 24 hrs. Mean trough levels ranged from 463 ng/mL (day 1) to 758 ng/mL (day 3). The conclusion was that a dose of 15 mg/kg i.m. in the Cynomolgus monkey would provide adequate blood levels for the planned safety study with trough levels remaining relatively constant.

3.6.5 One-Month Cynomolgus Monkey +-CsA

(Study number S08-10131, Valley Biosystems and MPI Research)⁵²

Two groups of 2 animals each were implanted with SB623 at a dose of 5 X 10^5 cells or vehicle. The striata of the left and right hemispheres of each animal received two injection tracts of 100 µL each consisting of five 20-µL implants. The right hemispheres of each animal received the cells, while the left hemisphere received vehicle only. One group of animals also received Cyclosporine A, 15 mg/kg/day I.M. beginning two days prior to surgery, while the other group received an equivalent amount of vehicle i.m. with the same schedule.

There were no clinical symptoms in the animals that could be attributed to SB623. There were also no adverse hematology or serum chemistry findings that could be attributed to SB623. The brain histological findings were that no SB623 cells were found at 1 month. Further, no histological differences were seen between the brains of any of the animals, or between the hemispheres of each animal.

The conclusions were that immunosuppression in this animal model did not prevent clearance of SB623 by one month and that there were no differences in pathology of the brains comparing with or without CsA.

3.6.6 6-Month Toxicity: Cynomolgus monkey

(Study number 1295-005; MPI Research)

The purpose of this GLP study was to assess the overall safety of SB623 after stereotactic implantation into brains of Cynomolgus monkeys. A total of 5 X 10^6 SB623 cells or vehicle was implanted each into the cortical left hemisphere and the subcortical right hemisphere in

12 normal female Cynomolgus monkeys, immunosuppressed with daily i.m. cyclosporine 15 mg/kg, with observations up to 6 months post-implantation.

Each hemisphere received 2 injection tracks, with each track consisting of two sites, each receiving 50 μ L, for a total of 200 μ L per hemisphere (5 million cells or vehicle), using a concentration of 25,000 cells/ μ L or vehicle. Animals (1 control, 3 cells each) were sacrificed at 1 mo., 3 mos., and 6 mos. post-implant.

The endpoints of the study were: clinical observations; clinical pathology at 2 weeks, 1 mo., 3 mos., and 6 mos.; histology of major organs (including brain); and cellular markers for presence of SB623, phenotype expression, and inflammation/immune responses.

No SB623 cells, as determined from an anti-human antibody or a Y-ish assay, were found at 1, 3 or 6 months.

There were no adverse, cell-related findings in clinical observations or clinical pathology. Histological examination of the brain and other organs and tissues showed no abnormalities that were attributed to SB623 cells.⁵³ Because no cells were found at any time point of this study, the biological relevance of these findings may be inconclusive. One animal in the 91-day recovery group and three animals in the 181-day recovery group that received SB623 cells had an area of necrosis in the external capsule adjacent to the putamen at one or both injection sites. Each area of necrosis measured approximately 1.0×0.5 to 3.0×0.5 mm in size and was characterized by loss of neuropil with associated reactive gliosis and minimal mononuclear infiltrate including gitter cells. The areas of necrosis observed in these animals were concluded to be most likely due to the act of injection rather than a direct test article effect.

3.7 Summary of Preclinical Safety Studies

See below Table 2 below.

		Group Size			
Study Reference	Study Description	(Species, sex)	Duration/Dose	Route of Admin.	Results/Conclusions
MPI 1295-002 (N-007)	Rat tumorigenicity study: 6 mos. and 12 mos. evaluation; athymic nude rat receiving anti-asialo antibody	60 males: equal control and cells 60 females: equal control and cells	One-time administration Total 0.5 million cells per animal (0.25 million per hemisphere, with 60% in striatum and 40% in cortex in each hemisphere)	Striatum and cortex	No tumors at either 6 mos. or 12 mos. No cell-related adverse findings during the study or at 6 mos. or 12 mos. No SB623 cells were seen at 6 mos.
MPI 1295-008	Rat tumorigenicity bridging study: 1 mo., 2 mos., 3 mos., and 4 mos.	30 animals: 3 per sex per time point	One-time administration Total 0.5 million cells per animal (0.25 million per hemisphere, with 60% in striatum and 40% in cortex in each hemisphere)	Striatum and cortex	No tumors at any time point to date (3 mos.) No cell-related adverse findings. SB623 cells were seen at 2 wks. but not at 1 or 2 mos
S08-10131	One-month pilot primate safety and SB623 survival comparing with/without CsA at 15 mg/kg/day i.m.	4 females	One time administration with or without CsA Total 5 million cells in the right hemisphere striatum and vehicle in the left hemisphere striatum using 2 injection tracts each with 5 implants.	Striatum	No SB623 cells were found at 1 month. No adverse clinical, laboratory, no histological findings attributable to SB623. No histological differences in the brains or hemispheres

Study Reference	Study Description	Group Size (Species, sex)	Duration/Dose	Route of Admin.	Results/Conclusions
MPI 1295-005 (N-018)	Cynomolgus monkey safety study: 1 mo., 3 mos., and 6 mos. evaluation CsA at 15 mg/kg i.m. daily	9 females with cells 3 females with control vehicle	One-time administration Total 10 million cells per animal (5 million cells per hemisphere in either cortical or subcortical areas)	Subcortical right hemisphere or cortical left hemisphere	No tumors at 1 mo., 3 mos., or 6 mos. No cell-related adverse findings during the study or at 1 mo., 3 mos. or 6 mos. No SB623 cells were seen at 1 mo., 3 mos., or 6 mos.

3.8 Summary of Known and Potential Risks and Benefits

No prior clinical studies with SB623 have been conducted. Based on the available animal data, no risks have been identified, but considerable potential benefit in reversing neurological deficits has been observed in a rat model of stroke.

4.0 DESCRIPTION AND JUSTIFICATION OF TREATMENT REGIMEN

4.1 Dosages

All dosages of cells are to be administered stereotactically through one burr-hole craniostomy using 3 needle tracks within and adjacent to the infarct and 5 cell deposits per track at varying depths, with 20 μ L per deposit. Concentrations of cell suspensions to be used will vary depending on the total dosage required per patient. See Table 3 below.

	Total SB623 Cells/Pt.	Total SB623 Cells/Deposit	Total SB623 Cells/Track	Concentration of SB623 Cells per Injection	Total Volume per Deposit, per Track, and Total	
Cohort 1	2.5 X 10 ⁶	1.65 X 10 ⁵	8.25 X 10 ⁵	8.3 X 10 ⁶ cells/mL	20 μL, 100 μL, and 300 μL	
Cohort 2:	5.0 X 10 ⁶	3.3 X 10 ⁵	16.5 X 10 ⁵	17 X 10 ⁶ cells/mL	20 μL, 100 μL, and 300 μL	
Cohort 3	10 X 10 ⁶	6.6 X 10 ⁵	33 X 10 ⁵	33 X 10 ⁶ cells/mL	20 μL, 100 μL, and 300 μL	

Table 3Dosages, Volumes and Cell Concentrations

4.2 Justification

Based on the animal pharmacology and safety studies (see Sections 3.2 and Section 3.6 above), particularly the primate study that used 10 million cells/animal, and considering the larger brain mass of humans, a maximum dose of 10×10^6 SB623 cells and a deposition volume of 20 µL are considered likely to be safe and have a good chance of showing some efficacy. The range of doses, as low as 2.5 X 10^6 SB623 cells, is considered necessary to observe any possible dose-response trends. The stereotactic surgery procedure to be used (see Section 7.0) has been shown to be safe and well tolerated in another similar study^{29,54}, and in a retrospective study.³⁰

The patient population of 6-60 months post-stroke was chosen to allow for stabilization of motor deficits, particularly after physical therapy, and to allow a sufficient number of patients for reasonable accrual. The duration of time needed for stabilization will vary by patient, with >95% stabilized at 3 mos. post-stroke.³⁰ Entry criteria to this study require demonstration of stable motor deficit(s) during the prior 3-week period.

5.0 NO CYCLOSPORINE A

5.1 Rationale

Protocol SB-STR01 Amendment 5.0 11-Sep-14

The toxicity properties of CsA are well known and present serious risks to patients, particularly older ones. Although most of the toxicity studies summarized in Section 3.6 used CsA, this was done to maximize the chances of uncovering any possible tumorigenicity properties of SB623. Subsequently, it was found that the presence of CsA was not relevant for the pharmacologic activity of SB623 in the MCAo stroke rat model (see Section 3.2.2). Although this is a xeno-transplant model, these findings suggested a need to re-evaluate the need for CsA in all future studies, including clinical. The other animal toxicity studies also indicated that even in immunosuppressed models, SB623 did not survive beyond a month or so, indicating clearance by means of an innate immune response rather than an adaptive one. Finally, an *in vitro* study has shown that SB623 possesses anti-inflammatory and immunosuppressive activity (see Section 3.2.1.6), thus suggesting the possibility that lack of use of CsA may not result in an adverse inflammatory response or any adverse cell-mediated immune response. Nevertheless, careful monitoring will be done to unsure safety of the patients (see below).

5.2 Monitoring for Humoral or Cell-Mediated Immune Response

In the Ph. 1/2a clinical study, Patients will be evaluated on Day 8 after implantation, monthly thereafter through month 4, and then at months 6, 9, 12 and 24 for any symptoms of inflammation, humoral immune response, or cell-mediated immune response (see Table 4). The parameters to be followed are: vital signs, hematology, serum chemistry, lipid panel, cytokine levels (TNF- α , IL-6, IFN- γ), CRP, head MRI, antibodies to SB623, and PBMC function (see Section 15.0).

6.0 STUDY PARAMETERS AND OBJECTIVES

The overall objective of the study is to evaluate the safety and efficacy of SB623 cells stereotactically implanted in the brains of patients with stable stroke.

6.1 Parameters

- 6.1.1 Safety
 - Adverse events
 - Serious adverse events (SAE)
 - Periodic head MRI scans
 - Serum chemistry, hematology, SB623 antibodies to SB623, cytokines, and PBMC function
- 6.1.2 Efficacy
 - Clinical Stroke Evaluations: European Stroke Scale (ESS),³¹ NIH Stroke Scale (NIHSS), Modified Rankin Score (MRS), Fugl-Meyer Score,³⁸ Cognitive Battery (see Appendix D, Section 1.0, Table 7).
 - Uptake of fluorodeoxyglucose measured by positron emission tomography (FDG-PET)

6.2 Objectives

6.2.1 Primary Objective

The primary objective is to determine acute and long-term safety of SB623 cells administered stereotactically around the infarct region of brains of patients with stable ischemic stroke.

6.2.2 Secondary Objectives

- To estimate clinical improvement of patients primarily with the ESS and secondarily with the NIHSS, the MRS, the Fugl-Meyer Score and Cognitive Tests
- To estimate metabolic improvement in and around the infarct region using FDG-PET

7.0 SURGICAL AND IMPLANTATION PROCEDURES

The surgical procedure is a modification of one used earlier with another cell product,^{29,54} and which has been shown to have a high degree of safety in a retrospective study of over 2,600 patients undergoing stereotactic surgery over the course of 28 years at one major clinic.³⁰ On the morning of surgery, a standard stereotactic coordinate frame (Leksell Stereotactic System®, manufactured by Elekta⁵⁵) is to be applied to the head under local anesthesia and mild sedation. Either a head CT scan overlaid on the Baseline MRI or a head MRI scan alone is to be performed for stereotactic targeting. The MRI scans are to use insulated posts an RIF transmitter head, and 1.5 tesla. A safe trajectory is to be defined to enter a cortical gyrus, sparing a sulcus. Points are to be determined in the basal ganglia inferior to the stroke and beyond the stroke. Three needle tracks are to be determined with trajectories in the same paramedian plane spaced by 5-6 mm at the target

One burr-hole craniostomy (1-1.5 cm) is to be fashioned under local anesthesia. The dura is to be opened and a 1.8-mm outer-diameter. 15-cm long stabilizing cannula containing a removable solid stylet is to be inserted to a point just proximal to the penumbra of the stroke area. The solid stylet is then to be removed, followed by insertion into the stabilizing cannula of a 0.9-mm outer diameter, 19-cm. long, 20-µL volume Pittsburgh Implantation Cannula (previously qualified for product stability and delivery and provided by the Sponsor) down to the deepest target point for the first implantation. A total volume of 100 μ L of cell suspension is to be aspirated into a 100- μ L syringe through the implant cannula. The implantation cannula is then to be filled with cell suspension. Five 20-µL volumes of cells are to be injected slowly (approximately 10 μ L/min.) into 5 implantation sites, slowly withdrawing the stabilizing needle probe so that the implantations are spaced as equally as possible (intervals of 4-5 mm) with 2-3 implants within the penumbra distal to the stroke area and 2-3 implants within the penumbra proximal to the stroke area. The target locations will be selected by the site neurosurgeon and neurologist to be closest to the motor pathway based on the patient's own neuroanatomy. This procedure is to be repeated with 2 other needle tracks with different trajectories, inserted through the same burr-hole craniostomy.

After completion of the procedure, the patient will receive a CT scan and be admitted to a neurosurgical patient ward for 24 hour observation, during which it is recommended that the patient be on a flat bed with optimal hydration and keeping the subject's head as flat as possible for the next 24 hours. The patient will be discharged on the first post-operative day

unless complications require a longer stay. An MRI is to be done on the first post-operative day (Day 2; see Section 10.5) to insure there are no significant bleeding risks.

8.0 PATIENT SELECTION

8.1 Inclusion Criteria

- 1. Age 18-75 years
- 2. Documented history of completed ischemic stroke in subcortical region of MCA or lenticulostriate artery with or without cortical involvement, with correlated findings preferably by MRI or by CT if MRI is contraindicated
- 3. Between 6 and 60 months post-stroke, and having a motor neurological deficit
- 4. No significant further improvement with physical therapy/rehabilitation (confirmed by no change in NIHSS greater than ±1 within three weeks prior to enrollment)
- 5. Modified Rankin Score of 3 or 4
- 6. NIH Stroke Scale score of >7
- 7. Two evaluations during prior 3 weeks with no more than ±1 point change in clinical evaluation using the NIH Stroke Scale
- 8. Able and willing to undergo computed tomography (CT), magnetic resonance imaging (MRI), and positron-emission tomography (PET) scans of the head
- 9. Agree that use of antiplatelet, anti-coagulant, or non-steroidal anti-inflammatory drugs to be determined by the local medical staff and in accordance with the ACCP 2012 guideline "Perioperative Management of Antithrombotic Therapy: Antithrombotic Therapy and Prevention of Thrombosis, 9th Edition: American College of Chest Physicians Evidence-Based Clinical Practice Guidelines", if applicable¹, provided that no antiplatelet, anti-coagulant, or non-steroidal anti-inflammatory drugs are to be restarted after surgery until after the Day 8 MRI is read and determined to be safe to re-start
- 10. Normal emotional status; *i.e.*, no disabling psychological deficits
- 11. Ability of patient or legal authorized representative to understand and sign an Informed Consent

8.2 Exclusion Criteria

- 1. History of more than 1 symptomatic stroke
- 2. History or presence of any other major neurological disease
- 3. Cerebral infarct size $>100 \text{ cm}^3$ measured by MRI
- 4. Myocardial infarction within prior 6 mos
- 5. Known presence of any malignancy except squamous or basal cell carcinoma of the skin
- 6. History of CNS malignancy
- 7. History of seizures or current use of antiepileptic medication
- 8. Uncontrolled systemic illness, including, but not limited to: hypertension (systolic >150 mm Hg or diastolic >95); diabetes; renal, hepatic, or cardiac failure
- 9. Uncontrolled psychiatric illness, including depression (Hamilton Score >14)

- 10. Total bilirubin >1.5 mg/dL
- 11. Serum creatinine >1.5 mg/dL
- 12. Hemoglobin <10.0 g/dL
- 13. Absolute neutrophil count $<2000 / \text{mm}^3$
- 14. Lymphocytes <800 /mm³
- 15. Platelet count $<100,000/\text{mm}^3$
- 16. Liver disease supported by AST (SGOT) or ALT (SGPT) ≥2.5 x institutional upper limit of normal
- 17. Serum calcium >11.5 mg/dl
- 18. International Normalized Ratio of Prothrombin Time (INR) >1.2
- 19. Signs and symptoms of intracranial herniation or increased intracranial pressure
- 20. Acute intracranial hemorrhage
- 21. Use of neuroleptic drugs
- 22. Unexplained abnormal preoperative test values (blood tests, electrocardiogram [ECG], chest X-ray); patients with electrocardiographic evidence to suggest a recent myocardial infarction, major dysrhythmia, x-ray evidence of infection, atrial fibrillation, or congestive heart failure will be excluded
- 23. Participation in any other investigational trial within 4 weeks of initial screening and within 7 weeks of study entry
- 24. Botulinum toxin injection, phenol injection, intrathecal baclofen, or any other interventional treatments for spasticity (except bracing and splinting) within the previous 3 mos.
- 25. Ongoing use of herbal or other non-traditional drugs
- 26. Ongoing drug or alcohol abuse
- 27. Contraindications to head CT, MRI, or PET
- 28. Pregnant or lactating
- 29. Female patients of childbearing potential unwilling to use an adequate birth control method during the first 6 months of the study
- Presence of serum antibodies to donor SB623 cells with a Luminex value of >1000 MFI (Maximum Fluorescence Intensity): HLA Class I (HLA-A*23:PWMV, HLA-A*68:CGBR; HLA-B*45:FJH, HLA-B*53:KJW; or HLA-Bw4, HLA-Bw6; HLA-Cw*04:SSWB, HLA-Cw*16:01); or Class II (HLA-DRB1 *13:NGUB, HLA-DRB1 *16:02; HLA-DQB1*05:CHZY, HLA-DQB1*05:BK; HLA-DQA1*01:DVB, HLA-DQA1*X, HLA-DRB3,4,5: 3*03:01, HLA-DRB3,4,5: 5*02:02)
- 31. Any other condition or situation that the investigator believes may interfere with the safety of the subject or the intent and conduct of the study

9.0 INVESTIGATIONAL PLAN

9.1 Overall Study Design

This is an open-label study of stereotactic, intracranial injection of SB623 cells (SB623 cells) in patients with hemiparesis from stable ischemic stroke who have remained stable during the

prior 3 weeks (as documented by NIHSS assessments at weeks -3 and -1). Three cohorts will receive escalating singe doses of SB623, which are to be stereotactically implanted into grey or white matter sites adjacent to the infarct region. One burr-hole craniostomy will be created, and cells implanted using 3 needle tracks with 5 cell deposits for each track at varying depths. Cell implantation will be standardized as to volume (20 uL/deposit) and rate $(10 \,\mu L/min)$, with spacing between each implant of approximately 5-6 mm. Each deposit is expected to take approximately 2-3 minutes, with each needle track being completed within 15 minutes. Each cohort will consist of 6 subjects defined by an increasing total number of cells implanted. Safety will be monitored by the Investigator, Principal Monitor, Medical Monitor, and an external Data Safety Monitoring Board (DSMB). For the first cohort, a single patient will first be dosed, then evaluated over a 2 week period for safety prior to dosing the next member of this cohort. This 2-week interval will continue between each of the remaining members of the cohort. If the safety profile is acceptable for a cohort, and after review by the DSMB, the first patient in each subsequent, sequential cohort will be dosed, beginning 4 weeks after dosing of the last patient of the prior cohort. For the second and third patients in each of the subsequent cohorts, there will be an interval of 2 weeks after the prior patients prior to further enrollment.

Safety will be monitored by clinical symptoms, laboratory findings, and MRI brain imaging. Efficacy will be determined based on changes in the clinical measures of stroke and on FDG-PET brain imaging.

A dose-limiting toxicity will be defined as any grade 3 or 4 events which are at least possibly related to study product or administration procedure. If the first patient in a cohort has a dose-limiting toxicity attributable to the SB623 cells, then no further patients will be dosed in that cohort until a comprehensive evaluation has been conducted. If 2 of 6 patients in a cohort have a dose-limiting toxicity attributable to the SB623 cells, then no further patients will be dosed in that or other higher-dose cohorts. Each dose-limiting-toxicity will be evaluated by the DSMB. The DSMB shall be the final arbitrator for attributions.

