10.0 STUDY ASSESSMENTS

10.1 Schedule of Study Activities

Table 4 below lists the procedures to be followed throughout the course of the study.

Confidential and Proprietary

	Scr. 1	Scr. 2	Baseline ¹	Enroll ²	Cell Admin	Follow-Up Period						Last Eval.	
Study Day			-2 to-1	-1 to 1	1	2	8						
Study Week	-3	-1	1	1	1	1	2						
Study Month								End of 1 and 2	End of 3 and 4	End of 6	End of 9	End of 12	End of 24
Informed Consent	X ³												
Demographics	Х												
Inclusion/Exclusion	Х		Х										
Medical History	Х	X^4	X ⁵	X^6									
Medication History	Х	X^4	X ⁵	X^6									
Signs & Symptoms	Х	X^4	X ⁵	X^6									
Pregnancy Test ⁷	X ⁸		X										
Physical Exam.	Х		Х									Х	Х
Vital Signs	Х	Х	Х				Х	Х	Х	Х	Х	Х	Х
Chest X-Ray and ECG	Х												
Hematology (Section 15.3)	Х	Х	Х				Х	Х	Х	Х	Х	Х	Х
Serum Chemistry (Sect. 15.3)	Х	Х	Х				Х	Х	Х	Х	Х	Х	Х
INR	Х		Х										
Occult Malig. (Sect. 10.2.2)	Х												
Lipid Panel (Section 15.3)			Х				Х	Х	Х	Х	Х	Х	Х
Cytokines (Section 15.3)			Х				Х	X (mo. 2)	X (mo. 4)	Х	Х	Х	Х
Blood for HLA antibodies	X ⁹												
Head CT					Х								
ImagingHead FDG-PET			Х							Х		Х	Х
ImagingHead MRI	X ¹⁰		Х		X ¹¹	Х	Х	X	Х	Х	Х	Х	Х

Table 4 **Study Procedures Flow Chart**

- ⁶ Only changes since Baseline
- ⁷ Only for women of childbearing potential ⁸ Serum β-HCG at Screening; serum or urine β-HCG at Baseline

¹ Only after documentation of stable stroke by two evaluations within 3 weeks prior to study entry using the NIH Stroke Scale (no more than ± 1 point)

² Enrollment only after all inclusion and exclusion criteria are verified and the patient qualifies for the study

³ Prior to any study-related procedures

⁴ Only changes since Screen 1

⁵ Only changes since Screen 2

⁹ May also be done at a pre-Screen visit

¹⁰ May instead be done at a pre-Screen visit ¹¹ Or CT overlaid with MRI from Baseline

	Scr. 1	Scr. 2	Baseline ¹	Enroll ²	Cell Admin	Follow-Up Period							Last Eval.
Study Day			-2 to-1	-1 to 1	1	2	8						
Study Week	-3	-1	1	1	1	1	2						
Study Month								End of 1	End of 3	End	End	End	End
Study Month								and 2	and 4	of 6	of 9	of 12	of 24
Clinical Stroke Evaluations	X ¹²	X ¹²	Х					X	Х	Х	Х	Х	Х
Cognitive Questionnaire			Х							Х		Х	Х
Blood for antibodies to			Х				X	\mathbf{V} (max 2)	\mathbf{V} (ma \mathbf{A})	Х	Х	X	X
SB623 and for PBMCs			Л				Λ	X (mo. 2)	X (mo. 4)	Λ	Λ	Λ	Λ
Serum Antibod. (see Sect.													
15.6 for assay schedule)													
PBMC Function (see Sect.													

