10.5 Follow-Up Period (Study Day 2)

The following will be performed:

- Adverse Events
- Concomitant Medications (see Section 12.0)
- Head MRI (MRI must be read before re-starting any antiplatelet, anticoagulant, or non-steroidal anti-inflammatory agents)

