10.6 Follow-Up Period (Study Day 8)

The following will be performed:

- Vital Signs
- Hematology (Section 15.3)
- Serum Chemistry (Section 15.3)
- Lipid Panel (Section 15.3)
- Cytokines (Section 15.3)
- Head MRI
- Blood for antibodies to SB623 and peripheral blood mononuclear cells (PBMC) function assays and for storage of PBMCs (Section 15.7)
- Luminex assay for antibodies to SB623 and PBMC function assay
- Adverse Events
- Concomitant Medications (see Section 12.0)

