10.7 Follow-Up Period (End of Months 1, 2, 3, 4 ± 5 Days)

- Vital Signs
- Hematology (Section 15.3)
- Serum Chemistry (Section 15.3)
- Lipid Panel (Section 15.3)
- Plasma Cytokines (months 2, 4 only) (Section 15.3)
- Imaging (head MRI)
- Clinical Stroke Evaluations
- Blood for antibodies to SB623 and peripheral blood mononuclear cells (PBMC) function assays and for storage of PBMCs (Months 2, 4 only) (Section 15.7)
- Luminex assay for antibodies to SB623 and PBMC function assay (Months 2, 4 only)
- Adverse Events
- Concomitant Medications (see Section 12.0)

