7.4.5 Physical Exam

Physical exam of the following body categories occurs at screen 1; general appearance, skin, HEENT, neck (including thyroid), heart, lungs, abdomen, lymph nodes, extremities, neurological assessment, musculoskeletal system, and other as specified on CRF. Subsequent visits require physical exam assessment only if significant change since screen 1 occurs for one of the specified body categories. Weight is recorded at Screening 1, Follow-up Month 12, and End of Study.

A listing of physical exam assessments including weight will be included.

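### No standardised motor or neurological examination is scheduled between Baseline and Month 1, so the 2-week patient interval always ends, and the 4-week cohort interval can end, before the first re-examination comparable with Baseline

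*Protocol*

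**What the plan says.** Protocol 9.1 sets the pace of dosing. In cohort 1 a patient is dosed, "then evaluated over a 2 week period for safety prior to dosing the next member of this cohort", and the same spacing applies through the rest of that cohort. A new cohort follows DSMB review, "beginning 4 weeks after dosing of the last patient of the prior cohort". For cohorts 2 and 3 the text reads: "For the second and third patients in each of the subsequent cohorts, there will be an interval of 2 weeks after the prior patients"; the sentence ends by placing that interval ahead of further enrolment.

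The assessments inside those intervals are listed in Protocol Table 4 and Sections 10.5 to 10.7, and SAP Appendix 10.1 agrees:

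- Day 1, after implantation: head CT, adverse events, concomitant medications.
- Day 2: adverse events, concomitant medications, head MRI.
- Day 8: vital signs, haematology, chemistry, lipids, cytokines, head MRI, antibody and PBMC blood, adverse events, concomitant medications.
- End of Month 1 ±5 days: the first post-implant entry in the Table 4 row "Clinical Stroke Evaluations". That row is blank at Days 2 and 8.

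The physical examination is marked only at Screening 1, Baseline, Month 12 and Month 24. SAP 7.4.5 adds: "Subsequent visits require physical exam assessment only if significant change since screen 1 occurs for one of the specified body categories". Section 9.1 explains the pattern: safety is followed through symptoms, laboratory findings and MRI, while the stroke scales are assigned to efficacy.

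**The concern.** Safety is the primary objective (Protocol 6.2.1), no clinical study of SB623 came before this one (3.8), and Section 7.0 has the targets chosen as near the motor pathway as the patient's anatomy allows. Motor decline is therefore a central risk, whether from the cells or from the needle.

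The dosing rules depend on finding it in time. A dose-limiting toxicity is a Grade 3 or 4 event at least possibly related to product or procedure, and Section 14.0 acts on such an event in the first patient or in 2 of 6. In the motor row of Appendix C, Grades 2 and 3 both need demonstrable weakness; Grade 3 adds loss of function. These patients enter with hemiparesis and an NIHSS above 7, so new weakness is a change from Baseline, and it is hard to establish without repeating the Baseline examination. Section 16.1 has adverse events come from spontaneous report or open questions.

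As scheduled, the decision to implant the next patient rests on MRI, laboratory and reported-event data for the previous one, with no motor examination to set against Baseline.

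**Working it through.** The documents give no figure on this point. The one safety calculation, in Protocol 18.5 (under 5% chance of missing a toxicity at a true rate of 40% with 6 patients), reproduces as 0.6^6 = 4.67%. It says nothing about timing and is not used below.

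**Inputs.** Patient interval 14 days and cohort interval 28 days (9.1). Month 1 visit window ±5 days (10.7). The documents give no day number for the end of Month 1, so four readings are tried: 27 days after implant (Study Day 28, with implantation on Day 1), 28, 30 and 31. That range is an assumption.

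**Formulas**, in days after implant:
- Visit = month length − 5, + 0 or + 5.
- Gap after the patient interval = visit − 14.
- Further cohort 1 patients implanted = number of implants at 14, 28, 42, 56, 70 that fall strictly before the first patient's visit.
- Cohort lag = visit − 28 for the last patient of a cohort; a positive value means the cohort may open first.

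| Month 1 at day | Visit early / on time / late | Gap after day 14 | Further patients implanted | Cohort lag (days) |
|---|---|---|---|---|
| 27 | 22 / 27 / 32 | 8 / 13 / 18 | 1 / 1 / 2 | −6 / −1 / +4 |
| 28 | 23 / 28 / 33 | 9 / 14 / 19 | 1 / 1 / 2 | −5 / 0 / +5 |
| 30 | 25 / 30 / 35 | 11 / 16 / 21 | 1 / 2 / 2 | −3 / +2 / +7 |
| 31 | 26 / 31 / 36 | 12 / 17 / 22 | 1 / 2 / 2 | −2 / +3 / +8 |

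**Patient interval.** The gap is positive in every cell, from 8 to 22 days. The 2-week point always comes before the first scheduled examination.

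**Cohort interval.** The lag changes sign. Of the 11 permitted visit days, 4 (27-day reading) to 8 (31-day reading) fall after day 28.

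**Who is affected at escalation.** Cohort 1 to 2: only the last patient, because at minimum spacing the fifth was implanted 14 + 28 = 42 days before opening, past every window above. Cohort 2 to 3: more than one patient if patients 4 to 6 are implanted close together. With implants at 0, 14 and 28 and all three of patients 4 to 6 at day 42 (an assumption), up to 3 could lack the visit.

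**Within cohorts 2 and 3.** If the 2-week interval also follows patient 3 (implants at 0, 14, 28, then from 42), the count before the first patient's visit is again 1 or 2.

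**The case against.** The best reply is that motor harm is watched for, only not with a scale. Section 9.1 calls for evaluation over the 2 weeks and lists symptoms first. There is a CT after implantation and 24 hours on a neurosurgical ward (7.0), MRI and adverse-event review on Days 2 and 8, SAE reporting within 24 hours (16.5), expedited reporting of neurological deterioration (16.1), and DSMB evaluation of each dose-limiting toxicity and after two or more SAEs (synopsis; SAP 7.6). Section 16.1 also asks staff to stay alert to possible events. Grade 3 motor toxicity involves lost function, which a patient can report, and a report of weakness has to be graded, which leads to an examination.

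Most of this stands. A reader might infer that nothing before Month 1 checks for motor harm; the documents do not support that. What is missing is narrower: a scheduled, standardised examination that can be compared with Baseline. The ward stay specifies no such examination and discharge is planned for the first post-operative day. The conditional examination in SAP 7.4.5 needs a change to have been noticed already.

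A reader might also infer that all five remaining patients of cohort 2 or 3 could be implanted before the first is re-examined. That needs patients 3 to 6 all implanted on day 28. Only the intervals before patients 2 and 3 are spelled out, but the end of the sentence in 9.1 argues for a hold after patient 3 as well. The supportable count is 1 or 2.

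**Conclusion.** The point holds as a gap in the visit schedule. Under every reading of Month 1 tried, the 2-week interval ends 8 to 22 days before the first scheduled examination comparable with Baseline. This covers all of cohort 1 and at least patients 2 and 3 of later cohorts. At minimum spacing, 1 or 2 further patients are implanted in the meantime. What could pass unseen is motor worsening that is less obvious or goes unreported; no rate for it is given or assumed here.

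The cohort part is weaker. Opening can precede the last patient's visit by up to 8 days, or follow it. Both intervals are minimums, and DSMB review is required as well. A reader might infer that the DSMB would escalate without that patient's examination. The documents do not show this: SAP 7.6 leaves the DSMB's data and procedures to its charter, which is not among them. What can be said is that neither the protocol nor the SAP requires the examination first.

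No estimate, test or analysis population is affected. The change is recommended because it is cheap and bears on the primary objective in a first clinical study.

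**What to change.** 1. Add an NIHSS at the existing Day 8 visit, in Protocol Table 4, Section 10.6 and SAP Appendix 10.1. A pre-discharge NIHSS on Day 2 is optional; it should be read with recent surgery and bed rest in mind.
2. State in Protocol 9.1 that the Day 8 score is compared with Baseline before the next patient is dosed. Worsening of more than 1 point, the margin the protocol already uses for stability at entry, should prompt an examination, adverse-event grading and Medical Monitor review before dosing.
3. Open the next cohort no earlier than 4 weeks after the last implant, and only once the DSMB has the last patient's Month 1 stroke evaluation.

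Toxicity definitions and grades stay as they are.

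**Cost.** 18 short assessments (1 × 18), or 36 with Day 2 (2 × 18), on a scale sites already score at Weeks −3 and −1 and at Baseline. Each of the two escalations may wait about a week or slightly more: up to 7 days with a 30-day month or 8 with a 31-day month, plus data transfer, and longer if the visit is late. More transient post-operative events may be sent for review.
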